Visit (V)	V01	PC1	V02	PC2	V03	PC3	V04	V05*	PC4	V06	PC5 6-month safety follow-up
Trial timelines (approximate # of days [D])	D0	D8	D60	D68	D120	D128	D150	D300-390	D308	D330-420	D480-570
Visit / Phone contact intervals		V01 + 8	V01 + 60D	V02 + 8D	V02 + 60D	V03 + 8D	V03 + 30D	V03 + 180D*	V05 + 8D	V05 + 30D	V05 + 180D
Time windows (days)		+2	±14	+2	±14	+2	+14	±14	+2	+14	+14
Approximate age of subjects (months)	2		4		6		7	12-15		13-16	18 - 21
Informed consent	X										
Inclusion/exclusion criteria	X										
Collection of demographic data/body stature	X										
Medical history	X							X			
Vaccination history	X										
Physical examination and temperature†	X		X		X		X	X		X	
IRT contact	X		X		X			X			
Randomization/allocation of subject number	X										
Blood sampling (BL)‡ (approximate volume)								BL0002 (6 mL)	BL0003 (6 mL)		BL0004 (6 mL)
Injection (SP0202 or Prevnar 13)	X		X		X			X			
Routine pediatric vaccines											
Pentacel	X		X		X			-			
RotaTeq	X		X		X			-			
M-M-R _{II} and Varivax	-		-		-			X			

Visit (V)	V01	PC1	V02	PC2	V03	PC3	V04	V05*	PC4	V06	PC5 6-month safety follow-up
Trial timelines (approximate # of days [D])	D0	D8	D60	D68	D120	D128	D150	D300-390	D308	D330-420	D480-570
Visit / Phone contact intervals		V01 + 8	V01 + 60D	V02 + 8D	V02 + 60D	V03 + 8D	V03 + 30D	V03 + 180D*	V05 + 8D	V05 + 30D	V05 + 180D
Time windows (days)		+2	±14	+2	±14	+2	+14	±14	+2	+14	+14
Approximate age of subjects (months)	2		4		6		7	12-15		13-16	18 - 21
Other pediatric vaccine ENGERIX-B§	X		X		X			-			
30-Minute observation period	X		X		X			X			
Telephone contacts		X**		X**		X**			X**		X††
Diary card (DC) provided collected	DC1		DC2 DC1		DC3 DC2		DC4 DC3	DC5 DC4		DC5	
Memory aid (MA) provided checked										X	X
Injection Site Reactions & Systemic Events Assessment	Solicited injection site and systemic reactions: Day 0–7 after each injection Unsolicited adverse events: Day 0–30 after each injection										
Collection of reportable concomitant medications	X		X		X		X	X			
Trial termination record							X			X	
Reporting of SAEs and AESIs	Throughout the trial										

* V05 can take place up until subject reaches 15 months.

† Mandatory at injection Visit (before injection). For other visits: physical examination and temperature measurement will be performed if necessary, based on the health status of the subject.

‡ BL0003 is to be collected prior to injection of study and concomitant vaccines.

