- 6) Complete the end of study CRF of the CRB.
- 7) Provide the memory aid to the subject's parent / guardian.

Safety Follow-up Telephone Call (D180 + 14 days)

The investigator or authorized designee will:

1) Ask to the parent / guardian if the subject has experienced any SAE or AESI in the time since vaccination.

2) Complete the relevant CRF for this phone contact.

A follow-up visit can be arranged depending on the information recorded during the phone call.

Infants

Visit 1 (Day 0): Inclusion, Randomization, Blood Sample, and Vaccination

- 1) Give the subject's parent / guardian information about the study, answer any of her / his questions, obtain written informed consent, and give her / him a signed copy.
- 2) Obtain significant medical history about the subject.
- 3) Check vaccination history.
- 4) Obtain demographic data.
- 5) Check medications and record reportable medication ongoing at the time of inclusion.
- 6) Check inclusion and exclusion criteria for eligibility.
- 7) Conduct a physical examination, including, but not limited to, examination of the head (ear, nose, and throat), neck, heart, lungs, abdomen, and extremities. If a routine examination had been performed within the past week by a qualified health care provider, it does not need to be repeated unless there were changes in health status, in which case it may be limited to the affected area.
- 8) Take the subject's temperature. If the temperature is $\geq 38.0^{\circ}\text{C}$ / $\geq 100.4^{\circ}\text{F}$, postpone vaccination until the condition is resolved.
- 9) If the subject is eligible, contact the IRT for randomization, to obtain a subject number, and vaccine allocation.
- 10) Administer the following study vaccines. Each vaccine should be administered in an assigned location (see Operating Guidelines) and documented appropriately:

Table 5.3: Vaccinations and route of administration at V01, V02, and V03

Vaccine		Route of administration
SP0202 or Prevnar 13	Observer-blind but double-blind across SP0202	Inject IM into the anterolateral area of the thigh, preferably the right thigh
Pentacel	Open-label	Inject IM into the anterolateral area of the thigh , preferably the left thigh (ie, the opposite leg from that used for SP0202 or Prevnar)
ENGERIX-B	Open-label	Inject IM into the anterolateral area of the thigh , preferably the left thigh (ie, the opposite leg from that used for SP0202 or Prevnar)
RotaTeq	Open-label	Administer orally per instructions in the package insert

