When multiple vaccines are administered at a single visit, each vaccine should be administered at a different anatomic site. If vaccines are given in the same limb, the injection sites should be separated by 1 inch / 2.5 cm or more, so that any local reactions can be differentiated (40).

Pentacel and ENGERIX-B (as applicable) should be given in the same thigh. They should not be administered in the same thigh as SP0202 or Prevnar. For details see Operating Guidelines.

Failure to administer vaccines in the designated limb will not constitute a protocol deviation, but should be recorded as a comment in the vaccination form of the eCRF. If the vaccines are not administered in the recommended limb(s), this should be corrected for subsequent injections.

- 11) Keep the subject under observation for 30 minutes and report any reaction / event in the source document.
- 12) Record the date of injection, site of injection, route of administration, as well as the dose number of the vaccine.
- 13) Give the parent / guardian a DC1 to record any injection site and systemic AEs, together with instructions for its completion, including explanations on the definition and use of intensity scales for collection of AEs. Remind parents to carefully report any clinical signs / diagnosis experienced at the same time as the fever episode $> 39.5^{\circ}\text{C} / 103.1^{\circ}\text{F}$.
- 14) Give the parent / guardian a thermometer for rectal temperature measurements, and a ruler to measure the size of any injection site reactions, and go over the instructions for their use.
- 15) Arrange an appointment for V02 ($D60 \pm 14$ days). Remind the parent / guardian to expect a telephone call 8 days after V01 and to bring back the DC1 when they return for V02 at a specified date and time.
- 16) Remind the parent / guardian to notify the site in case of a serious medical event occurs.
- 17) Complete the source document and relevant CRFs for this visit.

Telephone Call 1 (8 [+2] days after Visit 1)

Note: If D8 falls on a weekend or a holiday, the telephone call may be made on the following business day.

- 1) Record relevant information concerning the subject's health status on the telephone contact form. If an SAE occurred, follow the instructions in [Section 10](#) for reporting it.
- 2) Remind the parent / guardian to do the following:
 - Complete the Day 0–7 pages of the DC1
 - Complete the remaining pages of the DC1, and bring them to V02
 - Notify the site in case of an SAE

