Visit 2 (60 [±14] days after Visit 1): Collection of Safety Information and Vaccination

- 1) If the DC1 information from Day 0–7 has not yet been obtained, obtain it at this time by interviewing the parents. Review the pages of the DC1 with the parent / guardian, including any AEs, medications, or therapy that occurred since vaccination.
- 2) Check medications and record reportable ongoing medications.
- 3) Conduct a physical examination, including, but not limited to, examination of the head (ear, nose, and throat), neck, heart, lungs, abdomen, and extremities. If a routine examination had been performed within the past week by a qualified health care provider, it does not need to be repeated unless there were changes in health status, in which case it may be limited to the affected area.
- 4) Take the subject's temperature. If the temperature is $\geq 38.0^{\circ}\text{C}$ / $\geq 100.4^{\circ}\text{F}$, postpone vaccination until the condition is resolved.
- 5) Contact IRT system for vaccine allocation.
- 6) Inject the following study vaccines. Each vaccine should be administered in an assigned location (see Operating Guidelines) and documented appropriately. Refer to [Table 5.3](#) for details on vaccinations and route of administration at V01, V02, and V03.

When multiple vaccines are administered at a single visit, each vaccine should be administered at a different anatomic site. If vaccines are given in the same limb, the injection sites should be separated by 1 inch / 2.5 cm or more, so that any local reactions can be differentiated ([40](#)).

Pentacel and ENGERIX-B (as applicable) should be given in the same thigh. They should not be administered in the same thigh as SP0202 or Prevnar. For details see Operating Guidelines.

Failure to administer vaccines in the designated limb will not constitute a protocol deviation, but should be recorded as a comment in the vaccination form of the eCRF. If the vaccines are not administered in the recommended limb(s), this should be corrected for subsequent injections.

- 7) Keep the subject under observation for 30 minutes and record any adverse reaction in the source document.
- 8) Give the parent / guardian a DC2. Remind parents to carefully report any clinical signs / diagnosis experienced at the same time as the fever episode $> 39.5^{\circ}\text{C} / 103.1^{\circ}\text{F}$.

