- 9) Arrange an appointment for V03 ($D120 \pm 14$ days). Remind the parent / guardian to expect a telephone call 8 days after V02 and to bring back the DC2 when they return for V03 at a specified date and time.
- 10) Remind the parent / guardian to notify the site in case of a serious medical event occurs.
- 11) Complete the source document and the relevant CRFs for this visit.

Telephone Call 2 (8 [+2] days after Visit 2)

Note: If D8 falls on a weekend or a holiday, the telephone call may be made on the following business day.

- 1) Record relevant information concerning the subject's health status on the telephone contact form. If an SAE occurred, follow the instructions in [Section 10](#) for reporting it.
- 2) Remind the parent / guardian to do the following:
 - Complete the Day 0–7 pages of the DC2
 - Complete the remaining pages of the DC2, and bring them to V03
 - Notify the site in case of an SAE

Visit 3 (60 [±14] days after Visit 2): Collection of Safety Information and Vaccination

- 1) If the DC2 information from Day 0–7 has not yet been obtained obtain it at this time by interviewing the parents. Review the pages of the DC2 with the parent / guardian, including any AEs, medications, or therapy that occurred since vaccination.
- 2) Check medications and record reportable ongoing medications.
- 3) Conduct a physical examination, including, but not limited to, examination of the head (ear, nose, and throat), neck, heart, lungs, abdomen, and extremities. If a routine examination had been performed within the past week by a qualified health care provider, it does not need to be repeated unless there were changes in health status, in which case it may be limited to the affected area.
- 4) Take the subject's temperature. If the temperature is $\geq 38.0^{\circ}\text{C} / \geq 100.4^{\circ}\text{F}$, postpone vaccination until the condition is resolved.
- 5) Contact IRT system for vaccine allocation.

- 6) Inject the following study vaccines. Each vaccine should be administered in an assigned location (see Operating Guidelines) and documented appropriately. Refer to [Table 5.3](#) for details on vaccinations and route of administration at V01, V02, and V03.

When multiple vaccines are administered at a single visit, each vaccine should be administered at a different anatomic site. If vaccines are given in the same limb, the injection sites should be separated by 1 inch / 2.5 cm or more, so that any local reactions can be differentiated (40).

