12.2.3 Per-Protocol Analysis Set

The per-protocol analysis set (PPAS) is a subset of the FAS. Three PPAS will be defined: one for Toddlers (PPAS1), one for Infants at Primary series (PPAS2) and one for Infants at Booster (PPAS3).

The subjects presenting with at least one of the following relevant protocol deviations will be excluded from the PPAS1-Toddlers:

- Subject did not meet all protocol-specified inclusion criteria or met at least one of the protocol-specified exclusion criteria
- Subject did not receive vaccine
- Subject received a vaccine other than the one that he / she was randomized to receive
- Preparation and / or administration of vaccine was not done as per-protocol
- Subject did not provide the post-dose serology sample V02 in the proper time window or a post-dose serology sample was not drawn
- Subject received a protocol-prohibited medication or vaccine (identified among category 2 and 3, see [Section 6.7](#))

In addition to the reasons listed above, subjects will also be excluded from the PPAS1 if their V02 serology sample did not produce a valid serotype specific IgG test result (ie, results for all serotypes are missing).

The subjects presenting with at least one of the following relevant protocol deviations will be excluded from the PPAS2 Infants Primary series:

- Subject did not meet all protocol-specified inclusion criteria or met at least one of the protocol-specified exclusion criteria
- Subject did not complete the vaccination schedule
- Subject received a vaccine schedule other than the one that he / she was randomized to receive
- Preparation and / or administration of vaccine was not done as per-protocol
- Subject did not receive vaccine in the proper time window
- Subject did not provide the post-dose serology sample V04 in the proper time window or a post-dose serology sample was not drawn
- Subject received a protocol-prohibited medication or vaccine (identified among category 2 and 3, see [Section 6.7](#))

In addition to the reasons listed above, subjects will also be excluded from the PPAS2 if their V04 serology sample did not produce a valid serotype specific IgG test result (ie, results for all serotypes are missing).

The subjects presenting with at least one of the following relevant protocol deviations will be excluded from the PPAS3-Infants Booster dose:

- Subject did not meet all protocol-specified inclusion criteria or met at least one of the protocol-specified exclusion criteria

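### The infant Dose 3 visit (V03) is booked on study day 120 ±14 in one protocol step but on V02 + 60 ±14 days elsewhere, and PPAS2 does not give its window in days

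*Protocol*

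**What the plan says.** Day 0 is V01: the infant visit is headed "Visit 1 (Day 0): Inclusion, Randomization, Blood Sample, and Vaccination" (Protocol Section 5.1.4). For Dose 2 the booking step ("Arrange an appointment for V02 ($D60 \pm 14$ days") and the heading ("Visit 2 (60 [±14] days after Visit 1") describe the same window, because both count from V01.

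For Dose 3 they do not. Step 9 of infant Visit 2 says "Arrange an appointment for V03 ($D120 \pm 14$ days", whereas the heading that follows is "Visit 3 (60 [±14] days after Visit 2): Collection of Safety Information and Vaccination". Both infant Tables of Study Procedures (before and from Version 5.0), repeated as SAP Tables 3.4 and 3.5, give the V03 interval as V02 + 60 days with a ±14 day window. The same tables also show D120, in a row labelled "Trial timelines (approximate # of days [D".

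Protocol Section 5.2.7.1 requires a postponed infant dose to stay within the vaccination timeframe in the Table of Study Procedures.

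One of the PPAS2 exclusions in Protocol Section 12.2.3 is "Subject did not receive vaccine in the proper time window". SAP Section 5.2.1 carries the same item. Neither says which days count as proper for V03. The booster set, PPAS3, does spell out its window: 12-15 months of age and V03 + 180 days (±14).

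**The concern.** The two rules for Dose 3 have different anchors. One is a fixed study day; the other moves with the actual date of Dose 2. They give the same window only when V02 falls exactly on D60.

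Step 9 is what site staff follow when making the appointment, and it attaches its own ±14 days to D120. A site can therefore obey it exactly and still give Dose 3 of the PCV, Pentacel and RotaTeq outside the interval in the tables.

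What is at stake in the analysis is PPAS2 membership. SAP Section 5.2.5 runs immunogenicity first on the per-protocol sets, so PPAS2 leads for the post-Dose 3 IgG results. An infant vaccinated in good faith under step 9 may be removed from that set. Because the criterion gives no days, whoever derives PPAS2 has to take the window from elsewhere in the documents.

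**Working it through.** **Inputs**
- V01 = D0; V02 = D60 ±14 (Protocol 5.1.4, booking step and heading).
- Rule A, V03 = D120 ±14 (infant Visit 2, step 9).
- Rule B, V03 = V02 + 60 ±14 (Visit 3 heading; procedure tables in both documents).
- Evaluable infants per group after Dose 3: 140 (Protocol 12.5, SAP 5.5).

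**The plan's own figure.** Nominal V03 = 0 + 60 + 60 = D120, as in the tables. The nominal day is not in dispute; the windows around it are.

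**Permitted Dose 2 to Dose 3 interval**
- V02 range: 60 − 14 = D46 to 60 + 14 = D74.
- Rule A: V03 on D106 to D134. Shortest interval 106 − 74 = 32 days; longest 134 − 46 = 88 days.
- Rule B: 60 − 14 = 46 days to 60 + 14 = 74 days. V03 can fall from 46 + 46 = D92 to 74 + 74 = D148.

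| V02 on | Rule A: V03 days (interval) | Rule B: V03 days (interval) | Days allowed by both |
|---|---|---|---|
| D46 | D106-D134 (60-88) | D92-D120 (46-74) | D106-D120 |
| D60 | D106-D134 (46-74) | D106-D134 (46-74) | D106-D134 |
| D74 | D106-D134 (32-60) | D120-D148 (46-74) | D120-D134 |

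So intervals of 32-45 or 75-88 days can satisfy A and fail B. V03 on D92-D105 or D135-D148 can satisfy B and fail A.

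**How many infants.** The documents give no distribution of visit dates, so the spread is an assumption. Let *a* be the deviation of V02 from D60 and *b* the deviation of the V02-to-V03 interval from 60 days, independent and each within ±14. Rule B holds by construction; rule A fails when |a + b| > 14.
- Even spread over whole days: 29 × 29 = 841 pairs. Pairs with a sum above 14 number 14 + 13 + … + 1 = 105, and the same below −14, so 210/841 = 25.0%.
- Normal spread truncated at ±14: SD 7 days, 10.3%; SD 5, 3.6%; SD 3, about 0.1%.
- Per group: 140 × 0.250 = 35 at the top; 140 × 0.001 = 0.1, about 0, at the bottom.

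The reverse case is an infant booked by step 9 who breaches the table interval. If *b* is instead the deviation of V03 from D120, the condition is |b − a| > 14. With symmetric spreads this gives the same percentages.

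**The case against.** The strongest reply is that step 9 is scheduling shorthand. Every infant booking step uses the nominal day label, and the tables call those labels approximate. They cannot all be literal limits: a V04 on D150 would come only 150 − 134 = 16 days after a V03 on D134, although the Visit 4 heading asks for 30 [+14] days after Visit 3. The fourth phone call is labelled D308, although V05 may fall anywhere in D300-390 and the call is due 8 days after it. Section 5.2.7.1 refers postponed doses to the Table of Study Procedures. The SAP never repeats ±14 days around D120, and PPAS3 counts its booster interval from the earlier visit. Most of this stands: the documents lean towards the V02-based interval as the table window.

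It does not remove the conflict. Step 9 puts a tolerance directly on D120, Section 5.2.7.1 speaks of postponement rather than booking, and PPAS2 does not refer to the table.

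A reader might infer that there are two rival definitions of PPAS2. The documents do not support that: the SAP shows only the V02-based interval with the ±14 window. The gap is that PPAS2 neither states it in days nor points to it.

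A reader might also infer that the primary comparisons are biased. That is not shown. The same wording applies to all four randomised groups, the analyses are descriptive with no hypothesis tested, immunogenicity is also analysed on the FAS, and FAS2 has no time-window condition.

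**Conclusion.** The inconsistency is real and the day arithmetic is exact: 32-88 days under step 9 read literally, 46-74 days under the heading and tables. The literal reading rests on D0 being V01, since step 9 does not itself name the anchor. The 32- and 88-day extremes require V02 and V03 at opposite ends of their windows.

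The main effect is that an infant booked under step 9 may be vaccinated outside the table window and lost from PPAS2. How often cannot be known from the documents. The range of about 0.1% to 25%, or about 0 to 35 of 140 per group, depends wholly on the assumed spread. The upper end needs visits spread evenly over both windows and should not be read as an expectation. The severity is minor.

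**What to change.** Reconcile step 9 of infant Visit 2 with the Visit 3 heading and the procedure tables so that V03 has one anchor throughout. Which anchor, and so which dose interval, is for the sponsor's clinical team; this review does not choose.

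Then state the resulting V03 window in days in the PPAS2 criterion, as is already done for PPAS3. Protocol Section 12.2.3 allows the exclusion list to be completed at SAP writing and before database lock. The wording should be fixed before the unblinded post-Dose 3 analyses (the first 350 randomised infants, then all infants), so that the window cannot be settled with group results in view.

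The cost is one protocol step and one SAP line. Some infants may change PPAS2 status; no new data and no change of analysis method are needed.

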5.1.5 Planned Study Calendar

The following dates are approximate. The actual dates may differ as, for example, the study will not start until all the appropriate regulatory and ethical approvals have been obtained.

Planned study period - FVFS (first visit, first subject) to LCLS (last contact, last subject):

- Toddlers: May 2020 to September 2021
- Infants: April 2021 to May 2023

Planned inclusion period - FVFS to FVLS (first visit, last subject):

- Toddlers: May 2020 to March 2021
- Infants: April 2021 to November 2021

Planned vaccination period for toddlers: May 2020 to March 2021

Planned primary vaccination period (V01-V02-V03) for infants: April 2021 to March 2022

Planned booster vaccination period for infants: February 2022 to December 2022

Planned end of study: June 2023

Planned date of final clinical study report: Q4 2023

5.1.6 Early Safety Data Review

The safety of investigational products will be continuously monitored by the Sponsor. An ESDR will be performed, the goal of which is to allow for a cautious, stepwise approach to vaccine administration.

The safety data collected will be entered into the CRB and summarized by the Sponsor. A blinded review will be performed by the SMT meetings. An unblinded review by the independent DMC will also be conducted. It is understood that this review is based on preliminary data that have not been subject to validation and database lock. The usual and ongoing process of monitoring safety signals outside of those specified in the protocol-defined early interim safety analysis will continue unchanged.

The following safety parameters will be assessed as part of the ESDR:

- Immediate unsolicited systemic AEs
- Solicited injection site and systemic reactions
- Unsolicited AEs reported as related by the Investigator
- SAEs
- AESIs

Enrollment of infants will not begin until the end of the review. In addition, the data will be examined for the following:

- Any deaths, regardless of causality
- Any vaccine-related SAEs
- AESIs
- Any signs of injection site necrosis or exfoliative dermatitis
- Grade 3 fever reported in more than 10% of subjects; presence of concurrent infectious disease will be documented.

If any of the above criteria are met, a decision based on the SMT and DMC recommendations will be made as to whether enrollment of infants will be allowed to begin or whether any adjustments ought to be done (eg, an SP0202 formulation should not enter Stage II of the study).

The DMC will review the unblinded data by group to be able to identify any trend for differences between each SP0202 formulation and Prevnar 13 for each safety criterion and overall safety profile. The DMC may recommend removing 1 or more SP0202 formulation from Stage II.

Moreover, the option of partial or full unblinding can be available to the Sponsor through an independent statistician, if required, for a further in-depth review of the data.

The Sponsor's SMT is empowered to recommend a pause in recruitment while it investigates any potential signal or concern. The clinical team and SMT will review the data being generated from the study at regular intervals for any new safety signals or safety concerns.

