An unsolicited AE is an observed AE that does not fulfill the conditions prelisted in the CRB in terms of diagnosis and/or onset window post-vaccination. For example, if headache between D0 and D7 is a solicited reaction (ie, prelisted in the protocol and CRB), then a headache starting on D7 is a solicited reaction, whereas headache starting on D8 post-vaccination is an unsolicited AE. Unsolicited AEs includes both serious (SAEs) and non-serious unsolicited AEs.

Injection Site Reaction:

An injection site reaction is an AR at and around the injection site. Injection site reactions are commonly inflammatory reactions. They are considered to be related to the product administered.

Systemic AE:

Systemic AEs are all AEs that are not injection or administration site reactions. They therefore include systemic manifestations such as headache, fever, as well as localized or topical manifestations that are not associated with the vaccination or administration site (eg, erythema that is localized but that is not occurring at the injection site).

Adverse Event of Special Interest (AESI):

An adverse event of special interest is one of scientific and medical concern specific to the Sponsor's product or program, for which ongoing monitoring and rapid communication by the Investigator to the sponsor can be appropriate. Such an event might warrant further investigation in order to characterize and understand it. Depending on the nature of the event, rapid communication by the study Sponsor to other parties (eg,, regulators) might also be warranted.

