9.1.1.3.5 Assessment of Causality

The Investigator will assess the *causal relationship* between each unsolicited systemic AE and the investigational product administered as either *not related* or *related*, based on the following definitions:

Not related – The AE is clearly / most probably caused by other etiologies such as an underlying condition, therapeutic intervention, or concomitant therapy; or the delay between vaccination and the onset of the AE is incompatible with a causal relationship; or the AE started before the first vaccination (screening phase, if applicable)

Related – There is a “reasonable possibility” that the AE was caused by the investigational product administered, meaning that there is evidence or arguments to suggest a causal relationship

Note: By convention, all AEs reported at the injection site (whether solicited or unsolicited) and all solicited systemic AEs are considered to be related to the administered product and therefore are referred to as reactions and do not require the Investigator’s opinion on relatedness.

Adverse events likely to be related to the product, whether serious or not, that persist at the end of the study will be followed up by the Investigator until their complete disappearance or the stabilization of the subject’s condition. The Investigator will inform the Sponsor of the date of final disappearance of the event or the date of “chronicity” establishment.

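### The early safety review's parameter list omits non-serious unsolicited systemic AEs judged not related, which weakens the DMC's by-group comparison for those events before infants are enrolled

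*Protocol*

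**What the plan says.** Protocol 5.1.6 and the matching synopsis entry name five parameters for the ESDR:

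- "Immediate unsolicited systemic AEs"
- "Solicited injection site and systemic reactions"
- "Unsolicited AEs reported as related by the Investigator"
- SAEs
- AESIs

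Only the third is limited by causality. The data are also examined for "Any deaths, regardless of causality", for vaccine-related SAEs, for AESIs, for injection-site necrosis or exfoliative dermatitis, and for frequent Grade 3 fever.

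On the DMC's task, 5.1.6 says: "The DMC will review the unblinded data by group to be able to identify any trend for differences". The comparison is each formulation against Prevnar 13, on every safety criterion and the overall profile. The DMC may recommend that a formulation not go forward to infants.

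Protocol 9.1.1.3.5 defines a not-related event as, among other things, one "clearly / most probably caused by other etiologies such as an underlying condition, therapeutic intervention, or concomitant therapy". Under Protocol 6.4 the staff who assess safety do not know which vaccine was given.

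SAP 5.4 describes the same review as an assessment by the SMT and the DMC of the D0 to D30 safety data of a (redacted) share of Stage I. It states no relatedness limit. The synopsis and Protocol 6.4 leave further detail to the DMC charter.

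**The concern.** The DMC has the randomised allocation and the investigator does not. An investigator judging one child at a time, blind to group, cannot see that an event clusters in one formulation. Every toddler also receives Pentacel at the same visit, so a systemic event has a ready alternative explanation, and the protocol's definition directs events explained that way to the not-related class. A difference between concurrently randomised groups is informative whatever the individual causality calls were.

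The list used at the gate is also narrower than the trial's own endpoint. Protocol 9.1.1.2 counts all unsolicited AEs up to 30 days, and the analyses in Protocol 12.1.1.2 and SAP 5.1.1.2 do the same.

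At stake is whether a non-serious systemic event that is more frequent with one formulation, but not recognised as vaccine-caused, is in front of the DMC before the first 2-month-old infants are dosed.

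**Working it through.** **1. The plan's own figures.** The only planning numbers are evaluable subjects per group (Protocol 12.5): 35 × 0.90 = 31.5, 175 × 0.80 = 140 and 175 × 0.70 = 122.5. Rounded down, these give the stated 31, 140 and 122. The documents give no event rate, detection target or count rule for unsolicited AEs in the ESDR, so every rate below is an assumption.

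**2. What the list covers.**

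| Event class | Listed whatever the causality call? | Source |
|---|---|---|
| Immediate (30-minute) unsolicited systemic AEs | Yes | Protocol 5.1.6 |
| Solicited reactions, D0 to D7 | Yes | Protocol 5.1.6 |
| SAEs, AESIs, deaths | Yes | Protocol 5.1.6 |
| Unsolicited injection-site AEs | Yes in effect: related by convention | Protocol 9.1.1.3.5 |
| Other unsolicited systemic AEs, judged related | Yes | Protocol 5.1.6 |
| Other unsolicited systemic AEs, judged not related | **No** | Protocol 5.1.6 |

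Protocol 9.1.1.1 confirms that "Unsolicited AEs includes both serious (SAEs) and non-serious unsolicited AEs", so the serious part of unsolicited AEs reaches the review through the SAE item. The last row is the gap. It includes fever, vomiting and similar terms when they start after D7, because they are then unsolicited.

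**3. A first illustration, and its limits.** Assume an event in 25% of one formulation and 5% of Prevnar 13, 35 per group, with a fraction f called related in both groups. Let X1 ~ Bin(35, 0.25f) and X0 ~ Bin(35, 0.05f), and compute P(X1 − X0 ≥ 5).

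| f | Expected counts | P(excess ≥ 5) |
|---|---|---|
| 1.0 | 8.8 vs 1.8 | 81% |
| 0.5 | 4.4 vs 0.9 | 31% |
| 0.3 | 2.6 vs 0.5 | 9% |
| 0.2 | 1.8 vs 0.4 | 2% |

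Two features inflate the fall. First, the cut-off of 5 is in no document and is held fixed while the counts shrink. At f = 0.5 an excess of at least 3 has probability 67% (2.8% if both groups have the Prevnar 13 rate). Second, background and vaccine-caused events are given the same chance of being called related. If instead 5% of background events and a fraction s of caused events (20% of children) are called related, the rates are 0.05 × 0.05 = 0.0025 and 1 − (1 − 0.0025)(1 − 0.20s). P(excess ≥ 5) is then 3%, 27% or 78% for s = 25%, 50% or 90%.

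**4. A second illustration with higher background.** Assume background unsolicited AEs in a proportion b of children, an independent vaccine-caused event in 20% of one formulation, 5% of background called related, and s as above. All-cause rates are b and 1 − (1 − b)(0.80). Related-only rates are 0.05b and 1 − (1 − 0.05b)(1 − 0.20s). Power is for a two-sided 5% comparison of two proportions, 35 per group.

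| b | All-cause | Related-only, s = 25% | s = 50% | s = 90% |
|---|---|---|---|---|
| 20% | 31.7% | 20.1% | 41.5% | 71.2% |
| 30% | 22.5% | 18.1% | 38.8% | 69.0% |
| 40% | 16.9% | 16.5% | 36.4% | 66.8% |

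The related-only rates in Prevnar 13 are 1% to 2%, where the normal approximation is poor. By Fisher's exact test at b = 30%, power is 17% for all-cause and 1%, 13% and 54% for related-only. The ordering therefore depends on how often investigators recognise a caused event. No hypothesis is tested in this trial; power serves here only as a yardstick for how visible a difference would be.

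**The case against.** The strongest case is that this is a defensible choice for a preliminary-data gate. Related events, plus unfiltered serious, immediate, special-interest and solicited events, keep background illness from swamping groups of 35, and step 4 shows the filter can sharpen the signal when recognition is good. Pentacel is given in all four toddler groups and attribution is made blind, so the filter favours no group. The charter may already supply all unsolicited AEs, and SAP 5.4 reads as if it does. Protocol 5.1.6 keeps routine signal monitoring running, and SAP 5.4 allows further unblinded DMC analyses.

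Most of this stands, and it rules out three readings that a reader might infer:

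- That the DMC sees only investigator-related unsolicited events. Immediate events, SAEs and AESIs are listed without that limit, and injection-site events count as related by convention.
- That the filter discards the randomised comparison. A blinded related-only count is still a comparison of randomised groups, with less complete capture.
- That an unrecognised event would certainly be missing until the later Stage I analysis. SAP 5.4, the unseen charter and the ongoing monitoring leave that open.

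It does not close the gap. Noise reduction argues for showing related events separately, not for leaving the others off the list. Blind attribution prevents bias between groups but does not restore lost sensitivity. An unseen charter cannot reconcile a protocol list and a SAP sentence that differ.

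**Conclusion.** The point holds in a narrow form. The ESDR list leaves out one class of event: non-serious, non-immediate, non-AESI unsolicited systemic AEs judged not related. For that class the DMC's by-group comparison is weakened but not removed. The list is narrower than the all-cause primary endpoint and does not match SAP 5.4. Whether the DMC in practice receives more cannot be settled without the charter.

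No single figure for the loss is supportable. The fall from 81% to 2% in step 3 comes from assumed rates, a fixed arbitrary cut-off and equal recognition of background and caused events. Step 4 shows that related-only counts can be less or more sensitive than all-cause counts. All illustrations also take 35 per group, the most the review could contain, since the share of Stage I reviewed is redacted. What does not depend on the assumptions is that showing both counts can only add information to the decision on infants. This is a cheap improvement, not a fault that undermines the gate.

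**What to change.** In Protocol 5.1.6 and the synopsis, replace the third parameter with: *All unsolicited AEs from D0 to D30, with those reported as related shown separately*. Supply them to the DMC by group, by SOC and PT. Align Protocol 5.1.6, SAP 5.4 and the DMC charter on this wording. If the charter already provides the all-cause table, cite it in 5.1.6.

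The events are already collected from D0 to D30, so no new data are needed. The cost is a wording change, one more DMC table, and some background events for the DMC to read past.
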